6.1. Randomization and Blinding

Patients will be randomized between two groups, the Methadone group (MG) and the Non-Methadone group (NG). Randomization tables will be generated using REDCap database. Randomization will be stratified by Center of data collection. The investigators evaluating the primary and secondary outcomes will be blinded to the group assignments. The study participants, pharmacists, physicians and nurses taking care of the patients will not be blinded.

Assignment of patients to study groups will be by random allocation by randomization tables. There will be two randomization tables, one for Memorial Hermann Cypress and the other for Memorial Hermann Texas Medical Center. Patients predetermined to receive methadone will receive oral methadone which comes in 5mg tablets. Tablets will be crushed and administered via the feeding tube if patients are still on enteral feeding at the time the medication is administered. Patients predetermined not to receive methadone will continue treatment following usual care per hospital weaning protocols.

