2.5 Outcomes

a. Primary

Proportion of patients on methadone that get extubated by day number 5 from the date of intubation

b. Secondary

Proportion of patients that develop prolonged QTC after administration of methadone. Others will be ICU length of stay, ICU mortality, hospital length of stay and hospital mortality.

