3.3. Inclusion Criteria

Patients will be enrolled only if they consented and they meet all of the inclusion criteria listed below.

- 1. Patients 18 years or older
- 2. Patients on IMV for more than 72 hours
- 3. Patients infused Fentanyl or Hydromorphone for more than 72 hours
- 4. Patients with evidence of reversal of process that caused respiratory failure, adequate oxygenation (PaO2/FIO2>200; Positive end expiratory pressure (PEEP)≤8 and Ph≥7.2
- 5. Patients hemodynamically stable
- 6. Patients with a failed single or multiple attempts at spontaneous breathing trials

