3.4. Exclusion Criteria

All subjects meeting any of the exclusion criteria at baseline will be excluded from participation.

- 1. Patients with history of opioid drug abuse
- 2. Patients receiving schedule II narcotics on a chronic basis for longer than 6 months prior to ICU admission or on other analgesic infusions other than Fentanyl or Hydromorphone
- 3. Patients with cervical spinal cord injury or neuromuscular disease
- 4. Patients with end stage liver disease at ICU admission (ie, International normalized ratio ≥2and not taking warfarin and/or a total serum bilirubin ≥1.5 times above normal limits
- 5. Patients with prolonged QTc interval ≥500
- 6. Patients with prior history of cardiac conduction defects or suddendeath
- 7. Patients with QTc increase of ≥60 milliseconds above the value of prior EKGs measured during current ICU admission
- 8. Patients with more than 5 days on IV analgesia
- 9. Patients intubated for more than 30 days
- 10. Patients without feeding tubes
- 11. Patients not receiving enteral feeding
- 12. Exclusion of patients in a comatose state
- 13. Exclusion of patients in Status Epilepticus
- 14. Exclusion of post-operative patients

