5. STUDY DESIGN

5.1. Summary of Study Design

The study is randomized clinical trial. The duration of the study is 2 years. Patients will be screened to confirm they meet study criteria. Consent will be obtained from the legal authorized representative. Initial demographic data will be obtained using REDCap Database. Patients will be randomized to either Oral Methadone tablets or Non-Methadone group. The control group will receive usual care with IV Fentanyl or hydromorphone per hospital protocols as on appendix 1. Patients on the methadone group will be started on Methadone 5mg, 10mg or 15mg every 8 hours depending on Fentanyl drip rate (0-100mcg/hr, 100-200mcg/hr or >200mcg/hr) or hydromorphone drip rate (0-1.5mg/hr, 1.5-3mg/hr, or >3mg/hr). The rate of Fentanyl or hydromorphone will be reduced by 25% initially. If patients require additional sedation later, this will be administered per usual care and the total amount of additional opioids will be documented and used for analysis as morphine milligram equivalents (MME). Likewise, patients could be weaned more than 25% if they showed signs of tolerance to lesser sedation.

At Subsequent encounters: Rate of Fentanyl or Hydromorphone drip will be reduced by 25% every 24 hours until the patient is extubated from the ventilator.

Continuous IV opioids for analgesia for patients on mechanical ventilation is routine clinical care and will not be denied to patients. Once patients are extubated oral methadone will be discontinued and patient monitored for any opioid withdrawal symptoms and treated per protocol as shown on appendix 2 based on their clinical opiate withdrawal scale (COWS) appendix 4. For those with a score of less than 25 oral methadone will no longer be required. For those with a COWS score of >25 methadone will be resumed for a short taper of 3 days. The above can be illustrated as on study protocol flow on Appendix 5 and details on methadone taper as on Appendix 2.

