7.5. Blinding

The investigators evaluating the primary and secondary outcomes will be blinded to the group assignments. The study participants, pharmacists, physicians and nurses taking care of the patients will not be blinded.

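### Day-5 extubation is decided at an unblinded bedside, and the readable text sets no common readiness testing after randomisation, so arm-dependent timing of testing is a bias risk of unknown size and direction

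*Combined protocol and SAP*

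**What the plan says.** Section 2.5 defines the primary outcome as "Proportion of patients on methadone that get extubated by day number 5 from the date of intubation". Section 10.1 plans for 50% with methadone against 20% without.

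On blinding, section 6.1 states: "The study participants, pharmacists, physicians and nurses taking care of the patients will not be blinded". Section 7.5 adds: "The investigators evaluating the primary and secondary outcomes will be blinded to the group assignments".

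Readiness conditions appear in section 3.3, as entry criteria. They cover reversal of the cause, PaO2/FiO2 above 200, PEEP of 8 or less, pH of at least 7.2, haemodynamic stability and "Patients with a failed single or multiple attempts at spontaneous breathing trials". Entry also requires "Patients on IMV for more than 72 hours". Section 3.4 excludes "Patients with more than 5 days on IV analgesia" and, separately, "Patients intubated for more than 30 days".

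After randomisation, sections 4.2 and 5.1 specify opioid handling: a 25% infusion reduction every 24 hours with methadone, and the usual hospital protocol in control. Section 5.1 closes with "The above can be illustrated as on study protocol flow on Appendix 5". That figure is not visible in the available text. Section 6 counts only permanent disconnection for weaning time and compares the arms with Cox regression.

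**The concern.** Extubation is an action that someone decides to take, after testing whether the patient is ready. The documents do not name who decides, but it is safe to infer the treating team, who know the arm. If they test methadone patients sooner because they expect them to wean, day-5 extubation rises with no drug effect. If they hold back because methadone is long-acting, a real effect is diluted.

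The two safeguards in the plan act elsewhere. Blinded evaluators classify an extubation that has already happened. The permanent-disconnection rule limits credit for premature extubation in the weaning-time analysis. Neither governs when readiness is tested, and the Cox analysis depends on the same bedside decision.

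The different opioid wean is the intervention and is not at issue. Only a difference in testing that arises because staff know the arm would be bias. Without screens recorded by arm, readers could not separate the two.

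**Working it through.** **1. Is there a common rule in the readable text?**
- Section 3.3: readiness conditions, at entry only.
- Sections 4.2 and 5.1: opioid handling after randomisation; no readiness screen, SBT schedule or extubation criteria for either arm. The training described in 4.2 covers methadone tapering, opioid weaning and withdrawal.
- Appendix 1: infusion titration only.
- Appendix 2: a P:F threshold for starting a sedation wean, and a daily sedation-interruption reminder under delirium. Neither is an extubation rule.
- Appendix 6: no field for SBT or readiness-screen dates or results.
- Not visible: the Appendix 5 figure and any hospital ventilator-weaning protocol.

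**2. The plan's own figure.** Section 10.1 gives 76 patients for 50% against 20%, two-sided 5%, 80% power. The arcsine formula gives 76 and the pooled-variance formula 78. Adding 5% dropout to 76 gives 80. The sample size is not in dispute.

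**3. How many daily tests fit before day 5?** Entry needs more than 72 h of ventilation.
- Day 5 ending at 120 h: 120 − 72 = 48 h at most, about two tests.
- Intubation date as day 0 and day 5 counted in full: up to nearly 144 h, so 144 − 72 = 72 h at most, about three tests.
- Some patients may have no window left, because the 5-day limit applies to IV analgesia while intubation may have lasted up to 30 days.

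**4. Cost of one missed test.** Assume an equal, independent pass chance p at each of k tests. Then rate = 1 − (1 − p)^k, and with one test fewer the rate is 1 − (1 − p)^(k−1).

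| Tests | Rate | p | Rate with one fewer | Loss (points) |
|---|---|---|---|---|
| 2 | 20% | 0.1056 | 10.6% | 9.4 |
| 2 | 50% | 0.2929 | 29.3% | 20.7 |
| 3 | 20% | 0.0717 | 13.8% | 6.2 |
| 3 | 50% | 0.2063 | 37.0% | 13.0 |

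**5. Effect on the test.** Exact binomial enumeration, 38 per arm, two-sided 5% chi-squared test without continuity correction, counting rejections in favour of methadone. If a share s of one arm misses one test, that arm's rate becomes rate − s × loss. The shares are assumptions.

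| Scenario | s = 0 | s = 25% | s = 50% |
|---|---|---|---|
| No drug effect (methadone 20%), controls miss one of two | 2.5% | 4.5% (control 17.6%) | 7.8% (control 15.3%) |
| No drug effect, controls miss one of three | 2.5% | 3.7% (control 18.5%) | 5.3% (control 16.9%) |
| 50% vs 20%, methadone patients miss one of two | 80% | 65% (methadone 44.8%) | 48% (methadone 39.6%) |
| 50% vs 20%, methadone patients miss one of three | 80% | 71% (methadone 46.7%) | 61% (methadone 43.5%) |

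In the two-test case the shift is about 1 or 2 extubations of 38 in control, and about 2 or 4 of 38 with methadone.

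**6. Patients with no window.** Let a fraction w have no window, with the overall rate unchanged and two tests for the rest. Then p = 1 − √(1 − rate/(1 − w)), and the loss is rate − (1 − w)p.
- Rate 20%, w = 50%: p = 1 − √0.6 = 0.2254. One test gives 11.3% overall, a loss of 8.7 points instead of 9.4.
- Rate 50%: the loss is 18.3 points at w = 25%, 14.5 at w = 40% and 0 at w = 50%. In the last case everyone with a window must be extubated, so p = 1 and a missed test costs nothing.

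The false-positive illustration barely depends on w. The power illustration depends on it strongly.

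**The case against.** The strongest reply is that the gap may not exist. Controls follow hospital weaning protocols and section 5.1 points to a flow figure, and neither is visible; what cannot be seen is not missing from the plan. A reader might infer that the trial has no extubation rule at all. The documents do not support that, so the point stays conditional and the fix may reduce to a cross-reference.

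Next, nothing in the documents shows SBT practice differing by arm. Entry requires a failed SBT, so these ICUs already perform them, and both arms meet the same physiological conditions at randomisation. A reader might infer that the result will be tilted towards methadone. Section 1 does say most of the ICU physicians already use an oral-methadone strategy, which makes expectations plausible, but that fixes neither direction nor size.

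The arithmetic is also open to challenge. The two-test window is only one reading of day 5, equal pass chances are assumed in patients who have already failed an SBT, and the power loss vanishes in the extreme no-window case. All of this stands. The figures show sensitivity and are not an estimate.

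Finally, the remedy is partial, since unblinded staff would perform and record the screens. That also stands.

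**Conclusion.** The point holds as a conditional risk worth a cheap change. The primary outcome depends on a decision by staff who, by safe inference, are the unblinded treating team. The readable text standardises readiness only at entry, and the existing safeguards do not reach the timing of testing. Size and direction of any bias are unknown.

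Under the stated assumptions, the chance of a false result favouring methadone rises from 2.5% to 4.5–7.8% with two tests, or 3.7–5.3% with three. Power falls from 80% to 65–48% with two tests, or 71–61% with three, and the power loss can shrink to nothing if up to half of the patients have no window left. These results rest on assumed missed-test shares of 25% and 50%, equal pass chances and 38 per arm.

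It would go too far to call the open-label design, or the different opioid wean, a flaw. The first is disclosed and the second is the intervention. Confidence is medium because Appendix 5 and the hospital ventilator-weaning protocols could not be read.

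**What to change.** In sections 4.2 and 5.1, require the same daily extubation-readiness screen in both arms, followed by an SBT if the screen is passed, using the ICUs' existing criteria. If Appendix 5 or a hospital protocol already contains this, a cross-reference is enough.

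Add to Appendix 6, where not already collected: whether the screen and SBT were done each study day, their results, and the date, time and reason of extubation. Report screens done per ventilator-day by arm as the check on conduct. The screen is due daily whatever the sedation level, so a difference between arms points to conduct and not to the drug. SBT counts should be descriptive only, because they depend on sedation and therefore on the drug.

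The cost is protocol wording, one more topic in the planned one-month training, a few daily fields and slightly less clinician discretion over timing. No extra patients and no change to the regimen are needed. The final extubation decision stays unblinded, so the risk is reduced and made measurable, not removed.

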6.2. Contraception and Pregnancy Testing

Patients that are pregnant or have a positive pregnancy test or are on oral contraception will not be enroll into the study since they are a vulnerable population screened for eligibility.

6.3. Storage and Drug Accountability

Neither the Pharmacy nor the nursing staff will be accountable for the drugs. Pharmacy will dispense medication as normal physician order for drugs administered. Information on drug administered will be retrieved from patient records.

7. TREATMENT

7.1. Rationale for Selection of Dose

Dose selection will be based on currently approved protocol which is attached as an appendix 2.

7.2. Study Drug Formulations

Drug will be dispensed to patients in form of oral tablets appendix 3.

7.3. Study Drug Administration

Drug to be used is Methadone. Warnings not to use the drug in patients with asthma, GI obstruction, paralytic ileus, renal impairment, hepatic impairment, pregnancy, debilitated patients, QT prolongation, Congestive heart failure, Seizures, alcohol abuse and CNSdepression.

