Patients will be randomized to either Oral Methadone tablets the interventional group or Control group that will receive usual care with IV Fentanyl or hydromorphone per hospital protocols. Patients on the methadone group will be started on Methadone 5mg, 10mg or 15mg every 8 hours via a feeding tube depending on Fentanyl drip rate (0-100mcg/hr, 100-200mcg/hr or >200mcg/hr) or hydromorphone drip rate (0-1.5mg/hr, 1.5-3mg/hr, or >3mg/hr), Appendix3. The rate of Fentanyl or hydromorphone will be reduced by 25% initially to bring patient to a desired RASS (Richmond Agitation Sedation Scale score) as requested by the physician. While the control group will Not get any medication and will be weaned off opioids as per usual care.

c. Rationale for Study Population

In order to test our hypothesis our population of target needed to be patients admitted to the ICU who have been on mechanical ventilation for more the 72 hours on sedation with opioids. This gives us the opportunity to be able to compare outcomes between those that will receive methadone to those that will not

d. Rationale for Study Design

A randomized control trial gives us the best tool devoid of selection bias as well as controlling for potential confounders.

#UTHealth Houston

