3.6. Subject Replacement

Yes, Subjects who drop out will be replaced.

#UTHealth Houston

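### Section 7.3 warns against methadone in renal or hepatic impairment, but such patients can be enrolled and the dose rule omits the reductions that the attached label asks for

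*Combined protocol and SAP*

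**What the plan says.** Section 7.3 (Study Drug Administration) states: "Warnings not to use the drug in patients with asthma, GI obstruction, paralytic ileus, renal impairment, hepatic impairment, pregnancy, debilitated patients". Its list then goes on to QT prolongation, heart failure, seizures, alcohol abuse and CNS depression.

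None of the eligibility sections (3.3, 3.4, 6.2) mentions renal function. Exclusion 4 in 3.4 covers the liver, at INR ≥2 without warfarin and/or total bilirubin ≥1.5 times normal, judged at ICU admission. Pregnancy, also on the 7.3 list, does have a matching rule in 6.2: "Patients that are pregnant or have a positive pregnancy test or are on oral contraception will not be enroll into the study".

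The dose is set in 1.2b, where patients are "started on Methadone 5mg, 10mg or 15mg every 8 hours via a feeding tube depending on Fentanyl drip rate" or the hydromorphone rate. Section 5.1 repeats it: "Patients on the methadone group will be started on Methadone 5mg, 10mg or 15mg every 8 hours depending on Fentanyl drip rate". On stopping, 5.1 says: "Once patients are extubated oral methadone will be discontinued and patient monitored for any opioid withdrawal symptoms".

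Section 7.1 names Appendix 2 as the basis for dose selection. The legible part of Appendix 2 gives a general caution for hepatic impairment and no renal note for methadone. Appendix 3 is the methadone label. Its section 8.6 calls for smaller starting doses and slow titration in hepatic impairment; 8.7 calls for smaller starting doses, a longer interval and slow titration in renal impairment.

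**The concern.** A patient with renal impairment, or with hepatic impairment short of the 3.4 threshold, can meet every entry criterion. Once that patient is randomised to methadone, 7.3 read literally says to withhold it, 1.2b and 5.1 say to give the standard tier every 8 hours, and the label says to give less (and, for the kidney, less often). The protocol does not say which prevails.

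Two things are at stake. The first is safety. Label section 8.5 says that the risk of adverse reactions may be greater when renal function is impaired, and 8.6 says that liver impairment may raise exposure after repeated doses. The second is consistency of the comparison. Under 6.1 the treating staff know the allocation, so a decision to withhold methadone because of 7.3 can arise in one arm only. Section 3.6 says "Yes, Subjects who drop out will be replaced" without defining a dropout, and neither section 6 nor section 10 says that patients are analysed as randomised.

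**Working it through.** The plan has no calculated figure on this point. Its sample size (76, or 80 with fallout) does not enter. The check sets the sections side by side and then works out the daily doses.

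**Step 1: instructions for an eligible patient randomised to methadone**

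| | Renal impairment | Hepatic impairment below the 3.4 threshold |
|---|---|---|
| 3.3, 3.4, 6.2 | no criterion; eligible | eligible |
| 7.3 | do not use | do not use |
| 1.2b, 5.1 | standard tier every 8 h | standard tier every 8 h |
| Appendix 2 (legible text) | silent for methadone | caution, no dose |
| Label 8.6, 8.7 | smaller dose, longer interval | smaller dose |

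If 7.3 is read as a precaution, its row drops out. The difference between the dose rule and the label remains, so the dosing point does not depend on reading 7.3 as a ban.

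**Step 2: daily dose under the written rule**

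Daily dose = tier dose × 24/8 = tier dose × 3. This gives 5 × 3 = 15 mg, 10 × 3 = 30 mg and 15 × 3 = 45 mg, whatever the renal or hepatic function.

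**Step 3: what an adjustment could look like**

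The label gives no figure for the reduction, so these are assumptions for scale.

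- Longer interval only, same tier every 12 hours: tier dose × 2 = 10, 20 or 30 mg a day. This is one third less at every tier (1 − 2/3).
- One tier lower, with the 8-hour interval kept for hepatic impairment and a 12-hour interval for renal impairment:

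| Tier | Written rule | Hepatic example, every 8 h | Renal example, every 12 h |
|---|---|---|---|
| 15 mg | 45 mg/day | 10 × 3 = 30 (33% less) | 10 × 2 = 20 (56% less) |
| 10 mg | 30 mg/day | 5 × 3 = 15 (50% less) | 5 × 2 = 10 (67% less) |
| 5 mg | 15 mg/day | 2.5 × 3 = 7.5 (50% less) | 2.5 × 2 = 5 (67% less) |

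The lowest tier has no tier beneath it. The last row uses 2.5 mg, which appears in the example taper in Appendix 2 and in label section 2.4 as the starting dose for a first opioid.

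Across these examples the reduction runs from one third to two thirds, so pharmacy has to choose the figure.

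**The case against.** Section 7.3 is probably a compressed label summary. It opens as a warning, and read as a ban it would bar debilitated patients and those with CNS depression, which is much of the population that 3.3 requires. This stands, and it is why the remedy is to reword 7.3 and not to enforce it.

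Clinicians can already adjust. Appendix 3 is attached and cited in 1.2b, Appendix 2 carries a hepatic caution, and 6.3 says "Pharmacy will dispense medication as normal physician order for drugs administered". That is true, but the plan does not say in whom, by how much, or that an adjusted dose is within protocol.

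The opioid infusion is titrated to a RASS target and may be cut by more than 25%, under ICU observation and with the patient ventilated. This partly offsets methadone accumulation, but it changes the infusion and not the methadone. The taper in Appendix 2 starts only once infusions have been off for 24 hours, and it is not tied to organ function.

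The hepatic exclusion reaches further than its end-stage label suggests, because raised bilirubin alone excludes. This narrows the hepatic gap but leaves the renal one untouched.

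The dose tables in Appendix 2 are partly illegible and the Appendix 5 flow is not shown, so a modifier may exist there. The claim is therefore limited to 1.2b and 5.1, which contain none.

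Drug remaining at extubation is not specific to impaired patients. The label gives a half-life of 8 to 59 hours in general and warns against abrupt stopping. This also stands, and no separate argument is built on extubation.

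**Conclusion.** The point holds for renal and hepatic impairment. Eligibility, the warning in 7.3, the dose rule and the attached label do not agree, and the dose rule is the part that departs from the label. It is a low-to-moderate safety and consistency correction that should be made. It rests on the legible text and on impaired patients being enrolled in some number, which the documents do not give.

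Three stronger readings are tempting, and the documents do not support them:

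- **A count of conditions.** A reader might note that 7.3 names 12 conditions, five of which have no entry criterion (asthma, renal impairment, debilitation, heart failure, alcohol abuse), and treat that as the finding. The items are unequal. The label contraindicates asthma only when it is acute or severe and the setting is unmonitored or lacks resuscitative equipment, which is not an ICU. QT is substantially screened by exclusions 5 to 7, with daily QTc recording. The tally is not a measure of the problem.
- **Bias in the comparison.** A reader might infer that patients will be removed from the methadone arm and replaced. No section directs this. It would need staff to act on 7.3 after randomisation and then class the patient as a dropout. The plan leaves this open and does no more than that.
- **Loss of power.** Without a prevalence or an event rate by renal or hepatic function, no effect on power or event rates can be derived.

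**What to change.** (a) Reword 7.3 as precautions that match Appendix 3.

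(b) Add to the dose rule in 1.2b and 5.1 a lower starting dose for hepatic impairment below the 3.4 threshold, and a lower starting dose with an interval longer than 8 hours for renal impairment. One example for renal impairment is the next lower tier every 12 hours, with a stated dose for patients already on the 5 mg tier. The investigators and pharmacy should confirm the renal threshold and the exact doses.

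(c) Move to 3.4 any condition that the investigators regard as a true bar, with a threshold, checked before randomisation in both arms.

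(d) State in 10.2 and 3.6 that a randomised patient whose methadone is reduced or withheld stays in the assigned arm for analysis and is not replaced.

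The cost is wording in 7.3, 1.2b, 5.1, 3.6 and 10.2, plus 3.4 and the screening form for anything moved there. A renal-function entry may also be needed on the data form, since its legible text has no separate field. The downside is a lower methadone dose in some impaired patients, and slightly fewer eligible patients only for conditions moved to 3.4.
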